Once randomised, controlled amounts of each of the three test products and a reference product (0.9M saline) will then be applied in duplicate to defined areas of skin (0.02 mL/cm^2 of each product) via cells within semi-occlusive patch system to the upper back of each subject. Each patch shall remain in place for 24 hours, after which it will be removed, and each test site evaluated and recorded by a trained evaluator for signs of cutaneous irritation.

Study products will then be reapplied to the skin test sites, and one series of test sites will be exposed to a controlled dose of UV radiation and the other series will not. Both the irradiated and non-irradiated sites will be evaluated immediately after completion of the UV exposure procedures and again the following day. This procedure shall be repeated twice-weekly for 3 weeks (a total of 6 patch applications per series).

Subjects will then enter a 2-week rest phase during where no interventions are made. This will be followed by a 24-hour challenge exposure of each study product under semi-occlusive conditions. Test materials will be applied to naïve test sites on the upper back in duplicate. Once the patch systems are removed, one series will be exposed to UV radiation and the other shall

not. Both sets of test sites will be evaluated by a trained evaluator for signs of cutaneous irritation immediately, 24, 48 and 72-hours after UV exposure of the irradiated sites.

Photo-irritant reactions are most often characterised by intense delayed erythema (i.e. an exaggerated sunburn reaction) and are frequently followed by hyperpigmentation and peeling of damaged skin. The acute aspects of photo-irritant reactions may begin within a few minutes to hours after irradiation and tend to resolve within a few days to weeks. Hyperpigmentation may take several months to years to clear. Whereas the acute aspects of photo-irritant reactions typically present soon after irradiation, photo-sensitisation reactions seldom occur after the first exposure to the photo-allergen. Since photo-sensitisation is an immunological process in nature, multiple exposures to the photo-activated allergen and a latent period of several days to weeks are typically required before the immune system is ready to respond. Once a subject has been sensitised, subsequent exposures to the photo-allergen and UV radiation will elicit cutaneous responses quite rapidly within 24-72 hours ([Beani 2017](#)).

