#### Success criteria:

A test product will be considered to have low photo-sensitisation potential if the proportion of subjects with a potential photo-sensitisation reaction are comparable for the test product and saline.

The hypothesis is that the study products will have low photo-sensitisation potential. Therefore, it is expected that the vast majority of responses will be negative. No formal statistical comparison between treatment groups shall be made.

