If a subject develops a score of 'Strong' (++) or greater at any point during the induction phase, the next patch will be applied to an adjacent naïve (i.e. previously untreated) site. If a score of 'Strong' (++) or greater occurs at the naïve site, no further patch applications will be made. Such reactive subjects will, however, progress to the rest and challenge phase unless, in the opinion of the Investigator, it would be unwise to do so.

**Wednesday:** Subjects will arrive at site after 24 ( $\pm 4$ ) hours after irradiation and will be seated for at least 15-30 minutes to the environment of standard room conditions (18-26°C) and instructed to avoid contact of the back area with any other surface. Test sites will be evaluated for signs of irritation by a trained, blinded evaluator as per grading scale [Table 15-2 \(Appendix 2\)](#).

Duplicate patches will then be applied to the back, please see Monday assessments for further details on patch application.

**Thursday:** Tuesday assessments to be repeated.

**Friday:** Subjects will arrive at site after 24 ( $\pm 4$ ) hours after irradiation and will be seated for at least 15-30 minutes to the environment of standard room conditions (18-26°C) and instructed to avoid contact of the back area with any other surface. Test sites will be evaluated for signs of irritation by a trained, blinded evaluator as per grading scale [Table 15-2 \(Appendix 2\)](#).

The process of patch applications, grading and UV-exposure shall be repeated for an additional two weeks.

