### **End of Study (Visit 23):**

At visit 23/Day 40, after the challenge phase is complete, a final clinical assessment by a qualified dermatologist will be performed to ensure that it is medically appropriate to exit each subject from the study. After all study assessments are completed, subjects will be discharged from the study site.

Additionally, the dermatologist will use the total body of data for a subject (any positive reactions which occurred over the challenge phase) to judge whether a positive reaction is a potential sensitisation reaction or not.

Adverse events and concomitant medications will be assessed throughout the study.

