### 8.10.1 Challenge Phase Randomisation

At visit 19, another randomisation number will be assigned to each subject that completed the induction phase using the IRT system. This randomisation number will be different from the one previously assigned at Visit 4 and will include the sites of applications of each treatment for the challenge phase. The test sites of study products application will be previously untreated (naive) skin sites in the back, between shoulder blade and waistline for the duplicate UV-irradiated and non-UV-irradiated patch systems.

Randomisation schedule for the challenge phase will follow a 4x4 Latin Square (Williams) design. An example of the randomisation schedule is shown below:

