#### **Events NOT meeting the AE definition:**

- Any clinically significant abnormal laboratory findings (if applicable) or other abnormal safety assessments which are associated with the underlying disease, unless judged by the investigator to be more severe than expected for the subject's condition.
- The disease/disorder being studied or expected progression, signs, or symptoms of the disease/disorder being studied, unless more severe than expected for the subject's condition.
- Medical or surgical procedure (e.g. endoscopy, appendectomy) is not the AE. The condition that leads to the procedure is an AE (e.g. appendicitis).
- Situations where an untoward medical occurrence did not occur (social and/or convenience admission to a hospital).
- Anticipated day-to-day fluctuations of pre-existing disease(s) or condition(s) present or detected at the start of the study that do not worsen.
- Any cutaneous (dermal) irritation or sensitisation reactions which occur within the patch application area and can be completely described by the scale in [Appendix 2](#) will not be recorded as AEs. Reactions to the patch or adhesive tape will also not be recorded as AEs.

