4.1 Populations for Analysis

4.1.1 Subject Disposition

Screen failures are defined as subjects who consent to participate in the clinical study but are not subsequently randomized. An enrolled subject is a subject who has signed informed consent and is eligible to proceed beyond the screening visit. There are two randomizations; one is at Visit 4 for the induction phase and one at Visit 19 for the challenge phase. The number of subjects screened, enrolled and randomized in induction and challenge phase will be presented in [Table 14.1.1](#).

[Table 14.1.1](#) will also display the number and percentage of screen failure subjects (subjects not randomized in induction phase) with reasons why subjects are not randomized in induction phase. Percentages for screen failure subjects will be based on the total number of

subjects screened. The number and percentage of subjects not randomized in challenge phase will be displayed and percentages based on the number of subjects randomized in induction phase.

Subjects who complete the study (complete both induction and the challenge phases) and who discontinue during the challenge phase will be broken down by reason for discontinuation. The percentages will be based on the total number of subjects randomized in challenge phase.

The number and percentage of subjects in the safety population will also be summarized and percentages based on the number of subjects randomized in induction phase. The summary will be presented for all subjects (overall).

Subject disposition including demographic data (age, sex and race), screening date, phase, start date of study product and time, subject status (completer, Yes/No), study completion/withdrawal date, duration (in days) in the study (defined as: [(date of completion or withdrawal – start date of study product) + 1], duration (in days) of study product (defined as: [(last date and time of study product - start date and time of study product)+1]) and the primary reason for withdrawal will be listed ([Listing 16.2.1.1](#)) by phase for randomized subjects.

Subject disposition information will be listed for non-randomized subjects ([Listing 16.2.1.2](#)), displaying subject number, demographic information (age, sex and race), screening date, reason for screen failure and any further details of reason for screen failure.

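### A subject kept out of challenge after a repeated '++' in induction cannot be a primary event, and the reaction is tabulated as (photo-)irritation without anyone having judged whether it was sensitisation

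*Protocol*

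**What the plan says.** **Stopping and progression.** Under Protocol 4.1 (Induction Phase), repeated in 9.2.1 and Appendix 2, a first score of '++' or greater moves the next patch to adjacent untreated skin. After that: "If a score of 'Strong' (++) or greater occurs at the naïve site, no further patch applications will be made". These subjects will "progress to the rest and challenge phase unless, in the opinion of the Investigator, it would be unwise to do so". Progression is therefore the default and holding back is a discretionary exception.

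**Who is classified for sensitisation.** Protocol 4.1 (End of Study) says that "the dermatologist will use the total body of data for a subject (any positive reactions which occurred over the challenge phase" to judge whether a reaction is potential sensitisation. SAP 4.4 likewise places the dermatologist's assessment (Yes, No, Unable to Determine) in the challenge phase.

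**Primary endpoint.** SAP 4.4.1.1 requires two things: the sensitisation box ticked 'yes' at the final challenge visit, and a UV-site maximum above the non-UV maximum within the challenge phase.

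**Subjects who leave early.** SAP 4.4 does not consider a subject who discontinues before the last visit for sensitisation or photo-sensitisation, but allows that subject into the irritation endpoints. SAP 4.5.1 groups a missing box with 'No' and 'Unable to determine', and uses induction and challenge scores together.

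**Success.** Protocol 3: "A test product will be considered to have low photo-sensitisation potential if the proportion of subjects with a potential photo-sensitisation reaction are comparable" with saline. There is no margin and no test. SAP 4.4.1.3 (Supportive Analyses) is marked not applicable.

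**The concern.** The stopping rule is a sound safety measure. The difficulty is what the analysis does with a subject to whom it applies and who is then not challenged.

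Two strong reactions, the second on fresh skin, give an investigator good reason to withhold challenge. They also make the subject a plausible primary event. The protocol's own account of photo-sensitisation is that "multiple exposures to the photo-activated allergen and a latent period of several days to weeks are typically required". Induction patches go on at Days 1, 3, 8, 10, 15 and 17, and gradings run to Day 19, which is 18 days after the first application. A late induction '++' can therefore be allergic, and nobody is asked to decide whether it is.

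The loss runs in one direction for each product. All four products sit on the same patch, so a held-back subject takes a possible event from the reacting product and a non-event from the others. If the reacting product is a test product, this favours comparability with saline. If saline were the reacting product, it would work the other way. Photo-sensitisation compared with saline is the only stated success criterion, and the protocol expects nearly all responses to be negative, so a single case shapes the primary row.

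**Working it through.** **No plan figure to reproduce.** Protocol 12.1 gives at least 40 randomised and at least 25 evaluable completers, without a power calculation. There is no alpha, effect size or margin.

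**Step 1. Apply the SAP rules to one reacting subject.** Inputs are SAP 4.4, 4.4.1.1 and 4.5.1, with the severity order '-' < '+?' < '+' < '++' < '+++'.

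| Case | Induction UV / non-UV maximum | Challenge | Box | SAP category | Primary numerator |
|---|---|---|---|---|---|
| A | '++' / '-' | UV '++', non-UV '-' | Yes | photo-sensitisation | 1 |
| B | '++' / '-' | not challenged | missing | photo-irritation | 0 |
| C | '++' / '++' | not challenged | missing | irritation | 0 |

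A and B can be the same person with the same skin response. Only the investigator's decision differs.

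**Step 2. The denominator.** The documents do not settle it. Protocol 12.2.6 and SAP 4.4.1.1 name the safety population. Protocol 12.2.9 and SAP 4.4.3 include dropouts up to discontinuation. SAP 4.4 says early leavers are not considered for the sensitisation endpoints. With 40 dosed subjects and one true case on a test product (exact Clopper-Pearson 95% limits):

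- case captured: 1/40 = 2.5% (0.1% to 13.2%)
- case lost, subject kept in the denominator: 0/40 = 0% (0% to 8.8%)
- case lost, subject removed: 0/39 = 0% (0% to 9.0%)

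The numerator falls from 1 to 0 under both readings. Saline, if it has no events, stays at zero.

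**Step 3. Scale, by assumption only.** Let p be the true photo-sensitisation rate and w the share of sensitised subjects held back. Neither is in the documents. If all 40 subjects are otherwise followed to the end, the chance that the primary row shows at least one event is 1 − (1 − p(1 − w))^40:

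| p | w = 0 | w = 10% | w = 25% | w = 50% |
|---|---|---|---|---|
| 2% | 55.4% | 51.6% | 45.4% | 33.1% |
| 5% | 87.1% | 84.1% | 78.3% | 63.7% |

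For example, with p = 5% and w = 25%: 1 − (1 − 0.0375)^40 = 78.3%. A small w costs little; a large w costs a good deal.

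**Step 4. What the other outputs would show.**

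- The reaction appears in the irritation rows of Table 14.2.2.1 and in Listings 16.2.6.1 and 16.2.6.2. A withdrawal reason would be in Listing 16.2.1.1.
- Table 14.2.1.1 is described with Yes, No and Unable to determine, and no category for reactions never assessed.
- The narratives in Listing 16.2.6.7 cover challenge-phase reactions only.
- Protocol 10.1 excludes from AEs "Any cutaneous (dermal) irritation or sensitisation reactions which occur within the patch application area and can be completely described by the scale", so the listing of AEs leading to withdrawal need not contain the case.
- In Table 14.1.1, subjects "who discontinue during the challenge phase will be broken down by reason for discontinuation". Those not randomised to challenge are given as a number and percentage, and the SAP text asks for no reasons.

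**The case against.** The strongest reply is that this path is rare and that the protocol steers away from it. Three places in the protocol send reactive subjects on to challenge. To lose a primary event, a subject must score '++' twice, be held back against the default, and be someone who would have been judged 'Yes' with a higher UV score at challenge. The documents give no frequency for any of these steps. This stands, and it limits the weight of the point.

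A second reply is that Protocol 1 assigns photo-irritation primarily to induction and photo-sensitisation primarily to challenge after a rest period. Counting an unchallenged induction '++' as a primary event would mix the two readouts. This also stands, and it is why the primary definition should not change.

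A reader might go further than the documents allow in four ways.

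- **That stopped subjects are barred from challenge altogether.** Protocol 8.10.1 says "another randomisation number will be assigned to each subject that completed the induction phase", which could be read as shutting out anyone whose patching was stopped. The specific rule in 4.1 expressly sends such subjects on, so this is loose wording in a randomisation paragraph and not a second exclusion route.
- **That 1/25 becomes 0/24.** The 25 in Protocol 12.1 are subjects who complete the entire study, and Protocol 4.4 defines completion as finishing all phases. A held-back subject is not one of them.
- **That the reaction is hidden.** It is not, as Step 4 shows. What is missing is a judgement on sensitisation.
- **That the success conclusion would reverse.** With no margin and no test, a single case against none might still be called comparable. The loss changes the primary row; whether it changes the judgement cannot be shown.

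Finally, the SAP does not say outright that a held-back subject counts as discontinued. The numerator does not depend on this: without a challenge score and a ticked box, the primary definition cannot be met.

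**Conclusion.** The point holds in a limited form. A subject held back from challenge after a second '++' cannot be a primary event. If treated as discontinued, that subject is not considered for either sensitisation endpoint, and the reaction is tabulated as photo-irritation or irritation by default. The exclusion depends on the outcome and, for a test product, any loss favours comparability with saline.

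The robust size is one primary event lost per truly photo-sensitised subject held back. The percentages rest on 40 dosed subjects and on assumed rates. If nobody is held back, nothing changes. This is an inexpensive improvement to the reporting and not a flaw that invalidates the primary endpoint.

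**What to change.** Leave the primary endpoint definition as it is and make these changes before unblinding, so that the handling of such a subject cannot look chosen after the fact.

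1. **SAP 4.4.1.3.** Replace the not-applicable entry with a descriptive sensitivity count, per product including saline. Suggested text: *The primary count will be repeated with each subject not challenged because of an induction skin reaction counted, for the reacting product, as potential photo-sensitisation if the induction UV-site maximum exceeds the non-UV-site maximum, and as potential non-photo-initiated sensitisation otherwise.*
2. **Table 14.2.2.1.** Add a per-product row: *not challenged after induction reaction; sensitisation not assessed*. These subjects are then not shown only as irritation.
3. **Table 14.1.1.** Give the reasons for not being randomised to challenge.
4. **Optional.** Ask the blinded dermatologist to complete the existing check-box and narrative for such a subject, for use only in the sensitivity count. Protocol 1.1 already permits unplanned visits, but this step extends the dermatologist's task and would need a short protocol change.

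Items 1 to 3 cost SAP wording, one table row, a few disposition lines and one short repeat count. The drawback is that the sensitivity count may include reactions that were only irritant. It should be labelled an upper bound and read beside the primary count.

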### **Rest Phase (2 weeks):**

Once the induction phase is complete, subjects will enter a 2-week rest phase, during which there will be no product or patch applications.

### **Challenge Phase (Visits 19-23):**

Once the rest phase is complete, subjects will return for the challenge phase (visits 19-23). Randomisation for challenge phase will occur on visit 19 (day 36). The order to which the study products are assigned to the cells within the patch system are randomised to reduce the opportunity for bias through outcomes observed in the induction phase.

The challenge phase will consist of a duplicate parallel series of product applications under semi-occlusive patches to 2 naïve areas (i.e. previously untreated) of the back, between the shoulder line and waist, and away from the spinal mid-line.

These areas will be evaluated by the trained, blinded evaluator prior to any patch application to provide a baseline for interpretation. Two patches containing study products as per the randomisation sequence for the subject's challenge phase, will then be applied.

**Monday/Tuesday:** After randomisation for the challenge phase all assessments as per the Induction phase are to be repeated.

**Wednesday/Thursday/Friday:** Further test site assessments for signs of cutaneous irritation will be conducted 24 ( $\pm 4$ ), 48 ( $\pm 4$ ), and 72 ( $\pm 4$ ) hours after UV exposure as per grading scale [Table 15-2 \(Appendix 2\)](#).

### **End of Study (Visit 23):**

At visit 23/Day 40, after the challenge phase is complete, a final clinical assessment by a qualified dermatologist will be performed to ensure that it is medically appropriate to exit each subject from the study. After all study assessments are completed, subjects will be discharged from the study site.

Additionally, the dermatologist will use the total body of data for a subject (any positive reactions which occurred over the challenge phase) to judge whether a positive reaction is a potential sensitisation reaction or not.

Adverse events and concomitant medications will be assessed throughout the study.

## **4.2 Rationale for Study Design**

Compatibility studies represent the first contact of the finished product in humans and seek to prove the safety of product under maximised conditions, with controlled amount and application area. The application of study products within a semi occlusive patch allows for a clinical assessment under maximized conditions and is globally accepted, being widely used in the literature.

There will be a blinded evaluator (trained on the ICDRG scoring system) to assess all patch sites for the duration of the study. The intensity of any visual signs of irritation will be recorded according to the quantity and grade of the reactions, [Table 15-2 \(Appendix 2\)](#). The trained evaluator is responsible for grading the reactions, and the trained evaluator's score will be considered is final.

This study will be conducted under the supervision of a dermatologist. Subjects will be assessed by a dermatologist as a prerequisite to enrolment, and again at study end. For products with specific safety appeals, the study must be followed up by a specialist (dermatologist) (ANVISA, 2012).

For each subject who presents a positive reaction (i.e. a reaction score of '+' or greater) in the challenge phase a blinded dermatologist will further classify the reaction as potential sensitisation (or not) at the final visit and provide a single narrative description to summarise the entirety of the subject's experience of the event. As sensitisation and irritation can occur in the challenge phase, it is possible to record a positive reaction in the challenge phase which is not a sensitisation reaction. The dermatologist must consider how the reaction presents/evolves over time, to ascertain whether it is characteristic of a sensitisation reaction. The dermatologist will record their opinion in the narrative and with a check-box in the CRF.

The narrative must include the test site, start and finish date of the event, a description of how the event evolves over time, any action taken (e.g. moved patch) and whether the dermatologist considers the reaction to be a potential sensitisation reaction. If a clear diagnosis cannot be made, then the dermatologist should include this in the narrative.

The acute aspects of photo-irritant reactions may begin within a few minutes to hours after irradiation and tend to resolve within a few days to weeks. Whereas the acute aspects of photo-irritant reactions typically present soon after irradiation, photo- sensitisation reactions seldom occur after the first exposure to the photo-allergen. Since photo-sensitisation is an immunological process in nature, multiple exposures to the photo-activated allergen and a latent period of several days to weeks are typically required before the immune system is ready to respond. Once a subject has been sensitised, subsequent exposures to the photo-allergen and light will elicit cutaneous responses quite rapidly within 24-72 hours ([Beani 2017](#)).

A subject may experience positive reactions in any of the following patterns:

1. At ONLY the UV-exposed site,
2. At ONLY the Non-UV-exposed site,
3. At BOTH the UV-exposed and non-UV-exposed sites.

The location of positive reactions will be determined after unblinding to determine whether a reaction is potentially photo-initiated:

- Positive reactions which occur at ONLY the UV-exposed site will be considered photo-initiated.
- Positive reactions which occur at ONLY the non-UV-exposed site will not be considered photo-initiated.
- Positive reactions which occur at BOTH the UV-exposed and non-UV-exposed sites will be considered photo-initiated if the maximum score at the UV-exposed site is more severe than the maximum score at the non-UV-exposed site. If the maximum score at the UV-exposed site is equal to or lower than the non-UV-exposed site, then it will not be considered photo-initiated.

The inclusion of evaluations at 24, 48 and 72-hours for duplicate sites treated with study products, with or without UVR, in a cumulative application via an induction phase, latent rest phase, and challenge phase, permits simultaneous evaluation of the potential for contact irritation, photo-irritation, contact sensitisation and photo-sensitisation.

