After the trained evaluator has graded all the patch cells according to the ICDRG scoring Table [15-2 \(Appendix 2\)](#), a blinded dermatologist will evaluate every positive reaction (defined as a score of '+' or greater) in the challenge phase to further classify it as potential sensitisation (or not) and provide a narrative description of the event. The location of positive reactions will be determined after unblinding to determine whether a reaction was potentially photo-initiated.

The objective of this clinical study is to assess the photo-irritation and photo-sensitisation potential of three developmental cosmetic formulations compared to a reference product (negative control) after duplicate, repeated semi-occlusive patch applications to healthy human subjects by following a conventional photo-irritation and photo-sensitisation methodology under supervision of a dermatologist.

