## 5.8 Trained Evaluator and Dermatologist Qualifications

The patch test site assessment will be conducted in a 2-step process:

**Step 1:** A trained, blinded evaluator will score the test sites for signs of irritation per ICDRG scale ([Appendix 2](#)) at all time points specified in the [study schedule](#). The trained evaluator score will be considered final. The trained evaluator does not need to be medically qualified. All practical efforts will be made to ensure the same trained evaluator will be used to evaluate all subjects in the study. The evaluator(s) will be trained by a dermatologist in the ICDRG scale, this will be documented in the site master file.

**Step 2:** For each subject who presents a positive reaction (i.e. a reaction score of '+' or greater) in the challenge phase a blinded dermatologist will further classify the reaction as potential sensitisation (or not) at the final visit and provide a single narrative description to summarise the entirety of the subject's experience of the event. As sensitisation and irritation can occur in the challenge phase, it is possible to record a positive reaction in the challenge phase which is not a sensitisation reaction. The dermatologist must consider how the reaction presents/evolves over time, to ascertain whether it is characteristic of a sensitisation reaction. The dermatologist will record their opinion in the narrative and with a check-box in the CRF.

The narrative must include the start and finish date of the event, a description of how the event evolves over time, any action taken (e.g. moved patch), and diagnosis (potential sensitisation reaction, or other as appropriate). If a clear diagnosis cannot be made, then the dermatologist should include this in the narrative.

A dermatologist will assess the overall subject eligibility at the Screening Visit and continued eligibility in the study at Visit 2 (if not combined) to ensure the subject is free of any pre-existing dermatological pathology. This will confirm if subjects would require any follow up assessments. Additionally, a final assessment at Visit 23 (Last Visit) by a qualified dermatologist will confirm if it is medically appropriate to exit the subject from the study at the final visit ([Edward and Norman, 1982](#)).

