4.4.1 Primary Endpoint

4.4.1.1 Primary Endpoint Definition

The primary analysis will be based on safety population.

The primary analysis will be based on the number of subjects with potential sensitization reactions considered photo-initiated (i.e. potential photo-sensitization reactions).

Potential photo-sensitization reactions are defined as a positive reactions meeting both of the following requirements:

- sensitization reported as “yes” at final visit of challenge phase (sensitization box ticked “yes” on eCRF)
- the maximum score of the UV-exposed site (across all visits) during the challenge phase > maximum score of the non-UV exposed site (across all visits) during the challenge phase

The number and percentage of subjects with potential sensitization considered photo- initiated reactions will be presented by product group in [Table 14.2.2.1](#). No formal statistical inference will be performed.

All potential sensitization reactions considered photo-initiated will be listed ([Listing 16.2.6.3](#)) for the safety population.

A frequency table will be presented for potential sensitization reactions (Sensitization (Yes), non-sensitization (No) and Unable to determine) regardless of photo initiation status by product group in [Table 14.2.1.1](#).

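### The unit of the sensitisation verdict is inconsistent, and its attribution to a product is undefined when two or more products react in one subject

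*Protocol*

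**What the plan says.** Protocol 4.2 sets the verdict at subject level: "For each subject who presents a positive reaction (i.e. a reaction score of '+' or greater) in the challenge phase a blinded dermatologist will further classify". What is classified is one reaction, in the singular, at the final visit. The dermatologist is then to "provide a single narrative description to summarise the entirety of the" episode in that subject. On recording: "The dermatologist will record their opinion in the narrative and with a check-box in the CRF". Protocol 5.8, 8.13, 9.2.1 and Appendix 2 say the same.

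Other places work per reaction. The Background and Rationale in Protocol section 1 says that "a blinded dermatologist will evaluate every positive reaction" in the challenge phase. Protocol 4.1 and 8.5.4 agree, and so in substance does footnote b to Table 1-1.

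The required narrative content also differs. Protocol 4.2 says: "The narrative must include the test site, start and finish date of the event". Protocol 5.8 says: "The narrative must include the start and finish date of the event", with no test site. Protocol 8.13, 9.2.1 and Appendix 2 omit the site too.

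SAP 4.4.1.1 reports the primary endpoint, and a Yes / No / Unable to determine table, by product group. The first requirement of the endpoint is a yes reported "at final visit of challenge phase (sensitization box ticked" yes), with no product or cell named. SAP 4.4 defines photo-initiation by comparing the subject's highest score at the UV-exposed site with the subject's highest score at the non-UV-exposed site. SAP 4.5.1 uses the same box for the secondary endpoints.

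**The concern.** Each subject carries four products in the challenge phase (three test products and saline), each on a UV and a non-UV patch, so there are eight cells. The primary endpoint needs a verdict for each subject and product. If the verdict exists only for the subject, it cannot hold a yes for one product and a no, or an unable to determine, for another. Protocol 4.2 itself expects both sensitisation and irritation in the challenge phase.

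The stake is the split of events between test products and saline. The success criterion (Protocol section 3, SAP 1.2) is that a product's proportion is comparable to saline's. It has no margin and no formal comparison, and nearly all responses are expected to be negative. A single misplaced subject is therefore visible in the result.

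**Working it through.** The plan states no power or precision figure to reproduce. The check compares the units used, applies the rules to small cases, and then gives the scale.

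**1. Units side by side**
- Verdict per subject: Protocol 4.2, 5.8, 8.13, 9.2.1, Appendix 2.
- Verdict per reaction: Protocol section 1 (Background and Rationale), Table 1-1 footnote b, 4.1, 8.5.4.
- Reporting per product: SAP 4.4.1.1 and 4.5.1.
- Maximum score worded per subject: SAP 4.4.
- Rule for assigning one verdict when several products react: none in either document.

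**2. The box, with assumed scores.** Serum UV '++' / non-UV '-', truly sensitisation. Lotion UV '+' / non-UV '-', truly irritant. Both have UV above non-UV.
- One box, yes: both count as photo-sensitisation. Serum is right and lotion is wrong.
- One box, no: both count as photo-irritation. Lotion is right and serum is wrong.

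One product of the two is misplaced either way.

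**3. The maximum score, with assumed scores and the SAP order '-' < '+?' < '+' < '++' < '+++'**
- Cancelled event: serum UV '++' / non-UV '-', judged sensitisation; lotion UV '+' / non-UV '++'. By product, serum is photo-initiated. By subject, the maxima are '++' and '++', a tie, so serum's primary event disappears.
- Created event: serum UV '++' / non-UV '-', judged irritant; lotion UV '+' / non-UV '+', judged sensitisation. By product, lotion's scores tie, so it is not photo-initiated. By subject, '++' exceeds '+', so lotion enters the primary endpoint.

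**4. How often two or more products react in the challenge.** Assume that each of four products has positive rate p, independently. P(at least 2) = 1 - (1-p)^4 - 4p(1-p)^3.
- p = 0.05: 1 - 0.8145 - 0.1715 = 0.014, or 1.4%. At n=25, about 0.35 subjects.
- p = 0.10: 1 - 0.6561 - 0.2916 = 0.0523, or 5.2%. At n=25, about 1.3 subjects.

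These are upper limits on the affected share under the assumption, because the box errs only when verdicts differ, and the maximum rule only when the products' UV patterns differ. Positive correlation within subjects would be expected to raise them.

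**5. What one subject is worth.** 100/25 = 4.0 points at the minimum evaluable number; 100/40 = 2.5 points at the minimum randomised number. Clopper-Pearson 95% intervals: 0/25 gives 0 to 13.7% and 1/25 gives 0.1 to 20.4%; 0/40 gives 0 to 8.8% and 1/40 gives 0.1 to 13.2%.

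**6. A side effect on secondary endpoints.** The irritation endpoints in SAP 4.5.1 pool induction and challenge scores, but require the box to be no, unable to determine or missing. A subject-level yes for one product would also drop another product's induction reaction from the irritation counts. This does not touch the primary endpoint.

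**The case against.** A reader might infer that a yes can never be tied to a product. The documents do not support that.
- Several protocol sections describe classification of each reaction, so the per-subject wording is one of two.
- The evaluator scores every site, SAP 4.5.1 lists all grades, and SAP 4.3 lists the product in each cell. If only one product reacts, the scores identify it.
- Protocol 4.2 requires the test site in the narrative.
- The single narrative may mean one account over time, not one verdict over all products.
- The Yes / No / Unable table by product group presupposes product-level verdicts.
- The eCRF layout and the list of data displays are not readable in the public text, so a box per cell may exist.

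A reader might also take the chance of a second reacting product as 1 - 0.95^3 = 14% or 1 - 0.90^3 = 27%. Those figures are right only given that one product has already reacted. They are not the share of subjects affected. Nor does every subject with two reacting products produce an error: if both reactions are of the same type, a shared verdict is correct.

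All of this stands, and it narrows the point. It does not remove it: neither document says that the box is completed per cell or product, and the SAP rules carry no product index.

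**Conclusion.** The concern holds as an inconsistency of unit with a specific consequence. Followed literally, the plan misclassifies one product when two products in a subject have different verdicts, and the subject-level maximum can add or remove a primary event. Where a single product reacts, attribution is sound.

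Few subjects should be affected: at most about 1.4% to 5.2% of subjects in the challenge phase, under assumed independent rates of 5% to 10%. The documents give no rates, so this range is only illustrative. The effect per subject is 4.0 points at n=25 or 2.5 points at n=40, which matters because the comparison with saline has no margin. Product-level verdicts were probably intended. The text should say so, because a single box cannot be split afterwards and four of the five narrative lists do not ask for the site.

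**What to change.** - **eCRF and protocol:** record Yes / No / Unable to determine once per subject and cell position (A-D), covering the UV and non-UV patch together. Both patches use the same product sequence, so this gives one verdict per subject and product. A box for each positive cell would allow two conflicting verdicts for one product. The dermatologist can see the position while blinded to product and irradiation.
- **Protocol wording:** use this unit wherever the verdict is described. Specify patch area and cell in the narrative lists of 5.8, 8.13, 9.2.1 and Appendix 2, in line with the test site that 4.2 already requires.
- **SAP 4.4, 4.4.1.1 and 4.5.1:** index both the verdict and the maximum-score comparison by subject and product. Link cell to product after unblinding, through the challenge randomisation for challenge data and the induction randomisation for induction scores, because the sequences differ.

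The cost is eCRF layout and wording. The dermatologist already reviews the positive reactions, so no visit, reader or unblinding is added. If the eCRF already works per cell, only the text changes. If not, the change must be in place before verdicts are entered at Visit 23.
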